1.0 Introduction

This Statistical Analysis Plan (SAP) describes the statistical analyses for ABBV-668 Study M21-446, a single-arm, open-label study to evaluate the efficacy and safety of ABBV-668 in subjects with moderate to severe ulcerative colitis (UC).

Study M21-446 examines the efficacy and safety of ABBV-668 **CCI** mg orally twice a day (BID) as treatment in adult subjects with moderately to severely active UC.

The analyses of pharmacokinetic endpoints and biomarker research endpoints will not be covered in this SAP.

The SAP will not be updated in case of administrative changes or amendments to the protocol unless the changes impact the analysis.

Unless noted otherwise, all analyses will be performed using SAS Version 9.4 (SAS Institute Inc., Cary, NC 27513) or later.

2.0 Study Objectives and Design

2.1 Study Objectives

The primary efficacy objective of the study is to demonstrate greater proportion of subjects achieving endoscopic improvement with ABBV-668 treatment in the Intent-to-Treat (ITT) Population, which consists of all enrolled subjects with at least one dose of study treatment, when compared with historical placebo group.

The hypothesis corresponding to the primary efficacy objective is that the proportion of subjects achieving endoscopic improvement with ABBV-668 treatment at Week 8 is greater than the historical placebo group. The estimand for the primary endpoint is defined as the difference in the proportion of subjects achieving endoscopic improvement at Week 8 without initiation or dose escalation of UC-related corticosteroids and without initiation of any targeted immunomodulators (TIM) therapy (including biologics and

non-biologics), regardless of premature discontinuation of study treatment, between the ABBV-668 treatment group in the ITT Population and the historical placebo group.

The secondary efficacy objectives are to evaluate the efficacy of ABBV-668 with respect to the secondary endpoints specified in Section 3.2.

The estimands corresponding to the secondary efficacy objectives are:

For each binary secondary endpoint specified in Section 3.2: The difference in the proportion of subjects achieving a response without initiation or dose escalation of UC-related corticosteroids and without initiation of any TIM therapy (including biologics and non-biologics), regardless of premature discontinuation of study treatment, between the ABBV-668 treatment group in the ITT Population and the historical placebo group.

2.2 Study Design Overview

Study M21-446 is a Phase 2a, multicenter, open-label proof of concept study to investigate the efficacy and safety of ABBV-668 in subjects with moderate to severe UC. The study contains a 30-day screening period, 16-week treatment period, and a 30-day follow up period from the last dose of study drug.

[figure not shown]
Approximately 40 subjects will be enrolled in this study.

An endoscopy is required at Screening, and at Week 8 to evaluate endoscopic improvement. In order to explore the time-course of ABBV-668 efficacy, subjects will continue through Week 16. An endoscopy will be performed at Week 16 for subjects:

- Who have an endoscopic sub-score ≥ 1 at the Week 8 endoscopy; or
- Who have an endoscopic sub-score of 0 at the Week 8 endoscopy AND have subsequent worsening of their disease (as assessed by the Investigator) after the Week 8 endoscopy.

The schematic of the study is shown in Figure 1.

Figure 1. Study Schematic

BID = twice a day

2.3 Treatment Assignment and Blinding

This is a single-arm, open-label study.

2.4 Sample Size Determination

The planned sample size is approximately 40 subjects.

A meta-analysis for historical placebo data from UC studies for tofacitinib (OCTAVE1/2), upadacitinib (Phase 2b and Phase 3; data on file), and ustekinumab (UNIFI) gives CCI improvement rate at Week 8. A prior placebo distribution that matches this overall rate and has a variance close to the variance of the rate estimate from CCI. The prior distribution for the ABBV-668 treatment group is set to Jeffreys non-informative prior *Beta* (0.5, 0.5). Assuming a response rate increase of 30% in the ABBV-668 group compared to historical placebo, a sample size of 40 subjects will provide more than 90% probability to demonstrate that the posterior probability of rate difference (ABBV-668 vs. external

placebo) > 0 is larger than 90%. The external placebo response may be updated if new placebo data from similar trials become available before the Primary Analysis database lock.

3.0 Endpoints

Definitions of Efficacy Endpoints

Clinical Remission per Adapted Mayo Score: stool frequency subscore (SFS) ≤ 1 , and not greater than Baseline, rectal bleeding subscore (RBS) = 0, and endoscopic subscore (ESS) ≤ 1

Clinical Response per Adapted Mayo Score: decrease from Baseline ≥ 2 points and $\geq 30\%$, PLUS a decrease in RBS ≥ 1 or an absolute RBS ≤ 1

Clinical Response per Partial Adapted Mayo Score: decrease from Baseline ≥ 1 points and $\geq 30\%$, PLUS a decrease in RBS ≥ 1 or an absolute RBS ≤ 1

Clinical Remission per Full Mayo Score: Full Mayo score ≤ 2 with no subscore > 1

Clinical Response per Full Mayo Score: decrease from Baseline ≥ 3 points and $\geq 30\%$, PLUS a decrease in RBS ≥ 1 or an absolute RBS ≤ 1

Endoscopic Improvement: Mayo endoscopic subscore (ESS) of 0 or 1. Note that evidence of friability during endoscopy in subjects with a Mayo ESS of 0 or 1 will confer an endoscopic subscore of 2.

Endoscopic Remission: Mayo ESS = 0

Histologic remission: Geboes score of < 2.0

Histologic-endoscopic mucosal improvement: Mayo ESS ≤ 1 and Geboes score ≤ 3.1

Mucosal Healing: endoscopic (Mayo ESS = 0) and histologic remission (Geboes score of < 2.0).

3.1 Primary Endpoint

The primary endpoint is the achievement of endoscopic improvement (Mayo ESS of 0 or 1) at Week 8.

3.2 Secondary Endpoints

The secondary endpoints are as follows:

- Achievement of clinical remission per Adapted Mayo score at Week 8.
- Achievement of clinical response per Adapted Mayo score at Week 8.
- Achievement of clinical response per Partial Adapted Mayo score at Week 8.
- Achievement of endoscopic remission at Week 8.

3.3 Additional Efficacy Endpoints

In addition, the primary and secondary efficacy endpoints will be analyzed at all other scheduled visits during which the assessments are measured. The following endpoints will also be evaluated at scheduled visits during which the assessments are measured, unless otherwise specified:

- Achievement of clinical response per Full Mayo score over time in subjects with a Full Mayo score of 6 to 12 at Baseline.
- Achievement of clinical remission per Full Mayo score over time in subjects with a Full Mayo score of 6 to 12 at Baseline (at visits with endoscopy).
- Achievement of SFS = 0, RBS = 0, and ESS = 0 over time (at visits with endoscopy).
- Achievement of SFS = 0, RBS = 0, and ESS \leq 1 over time (at visits with endoscopy).
- Time to clinical response per Partial Adapted Mayo.
- Achievement of SFS \leq 1 over time.
- Achievement of RBS = 0 over time.
- Change from Baseline in RBS over time.

- Change from Baseline in SFS over time
- Achievement of histologic-endoscopic mucosal improvement over time (at visits with endoscopy).
- Achievement of histologic remission over time (at visits with endoscopy).
- Achievement of mucosal healing (endoscopic and histologic remission) over time (at visits with endoscopy).
- Change from Baseline in number of extraintestinal manifestations (EIM) over time (as captured in the EIM electronic case report form [eCRF]).
- Change from Baseline in fecal calprotectin (FCP) over time.
- Achievement of FCP below 150 mg/kg over time.
- Achievement of FCP below 250 mg/kg over time.
- Change from Baseline in high sensitivity C-reactive protein (hs-CRP) over time.
- Achievement of no nocturnal bowel movements at Week 8 as assessed by the UC symptom daily diary.
Achievement of no nocturnal bowel movements at Week 16 as assessed by the UC symptom daily diary.
- Achievement of no tenesmus at Week 8 as assessed by the UC symptom daily diary.
Achievement of no tenesmus at Week 16 as assessed by the UC symptom daily diary.
- Change from Baseline in number of fecal incontinence episodes per week at Week 8 as assessed by the UC symptom daily diary.
Change from Baseline in number of fecal incontinence episodes per week at Week 16 as assessed by the UC symptom daily diary.
- Change from Baseline in number of days over a week with sleep interrupted due to UC symptoms at Week 8 as assessed by the UC symptom daily diary.
Change from Baseline in number of days over a week with sleep interrupted due to UC symptoms at Week 16 as assessed by the UC symptom daily diary.
- Change from Baseline at Week 8 in Inflammatory Bowel Disease Questionnaire (IBDQ) total score.
Change from Baseline at Week 16 in IBDQ total score.

- Achievement of no abdominal pain at Week 8 as assessed by the UC symptom daily diary.
Achievement of no abdominal pain at Week 16 as assessed by the UC symptom daily diary.
- Achievement of no bowel urgency at Week 8 as assessed by the UC symptom daily diary.
Achievement of no bowel urgency at Week 16 as assessed by the UC symptom daily diary.
- Change from Baseline at Week 8 in Functional Assessment of Chronic Illness (FACIT)-Fatigue.
Change from Baseline at Week 16 in FACIT-Fatigue.

3.4 Safety Endpoints

Safety measures monitored in the study include the following:

- Treatment-emergent adverse events (TEAEs), serious adverse events (SAEs), and AEs leading to discontinuation of study drug
- Safety topics of interest
- Potentially clinically significant laboratory and vital signs parameters
- Columbia-Suicide Severity Rating Scale (C-SSRS) parameters

4.0 Analysis Populations

The following populations will be used for the analyses.

The ITT Population consists of all subjects who received at least 1 dose of study drug.

The ITT Population will be used for all efficacy and Baseline analyses.

The Safety Population consists of all subjects who received at least 1 dose of study drug.

The Safety Population will be used for all safety analyses.

5.0 Subject Disposition

Enrollment failure subjects (i.e., subjects who consented to participate in the study but were not enrolled) and associated reasons for failure to enroll (e.g., screen failed [eligibility criteria not met], withdrawal by subject, etc.) will be tabulated for all screened subjects.

A summary of subject accountability by investigator will be provided where the number of subjects in each of the following categories will be tabulated for the treatment group:

- Subjects enrolled in the study;
- Subjects who took at least one dose of study treatment;
- Subjects who completed study treatment;
- Subjects who prematurely discontinued study treatment

The number and percentage of subjects in the ITT Population who prematurely discontinued study treatment will be summarized by primary reasons for not completing study treatment.

6.0 Study Treatment Duration and Compliance

For the Safety Population, duration of treatment will be summarized for ABBV-668 treatment group. Duration of treatment is defined for each subject as last dose date minus first dose date + 1 day. Duration of treatment will be summarized using the number of subjects treated, mean, standard deviation, median, minimum and maximum. In addition, the number and percentage of subjects in each treatment duration interval (≥ 15 days, ≥ 30 days, ≥ 45 days, ≥ 60 days, ≥ 75 days, ≥ 90 days, ≥ 105 days) will be summarized.

Treatment compliance will be summarized for the entire treatment period for the Safety Population. Treatment compliance is defined as the number of capsules actually taken divided by the number of capsules that should have been taken. Percent compliance will be summarized.

7.0 Subject Characteristics

Categorical variables will be summarized with the number and percentage of subjects. Continuous variables will be summarized with descriptive statistics (number of non-missing observations, mean and standard deviation, median, minimum and maximum).

7.1 Demographics and Baseline Characteristics

Demographics and Baseline or disease characteristics will be summarized descriptively for the ITT Population. Unless otherwise specified, Baseline is defined as the last non-missing value prior to the first administration of study treatment.

Continuous demographic variables include age, weight, height, and body mass index (BMI).

Categorical demographic variables include:

- Sex (Male, Female)
- Age Group 1 (< 40, 40 – 64, \geq 65 years)
- Age Group 2 (\leq median, $>$ median)
- Ethnicity (Hispanic or Latino, Not Hispanic or Latino)
- Race (White, Black or African American, American Indian/Alaska Native, Native Hawaiian or Other Pacific Islander, Asian, Other)
- Region (US, ex-US)
- Tobacco user (current, former, never, unknown)
- Alcohol user (current, former, never, unknown).
- BMI (normal: $< 25 \text{ kg/m}^2$, overweight: $\geq 25 – 30 \text{ kg/m}^2$, obese: $\geq 30 \text{ kg/m}^2$)

Continuous disease characteristics at Baseline include:

- UC disease duration (years)
- Full Mayo score and its components (stool frequency, rectal bleeding, Physician Global Assessment, and endoscopy subscores)

- Partial Mayo score
- Adapted Mayo score
- Partial Adapted Mayo score
- hs-CRP (mg/L)
- Fecal Calprotectin (μ g/g)
- Geboes score
- Number of extraintestinal manifestations
- IBDQ total and domain score
- FACIT-Fatigue score

Categorical disease characteristics variables at Baseline include:

- Baseline corticosteroid use (yes, no)
- Baseline immunosuppressant use (yes, no)
- Baseline aminosalicylates use (yes, no)
- Prior exposure to TIM therapy (including biologic and non-biologic) for UC (1, > 1)
- Prior inadequate response/intolerance to TIM therapy (including biologic and non-biologic) for UC (1, > 1)
- Baseline fecal calprotectin (≥ 250 mcg/kg, < 250 mcg/kg)
- Baseline Adapted Mayo score (≤ 7 , > 7)
- Baseline Full Mayo score (≤ 9 , > 9)
- Mayo endoscopic subscore (2, 3)
- Baseline hs-CRP (≤ 5 mg/L, > 5 mg/L)
- Disease duration Group 1 (≤ 3 years, > 3 years)
- Disease duration Group 2 (\leq median, $>$ median)
- Disease extent (rectosigmoid, left-sided, extensive/pancolitis)

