3.4 Additional Efficacy Endpoints

In addition, the primary and secondary efficacy endpoints will be analyzed at all other scheduled visits as noted in the Study Activities Table ([Appendix D](#)) during which the assessments are measured.

The following endpoints will also be evaluated at scheduled visits during which the assessments are measured as noted in the Study Activities Table ([Appendix D](#)), unless otherwise specified:

- Achievement of clinical response per Full Mayo score over time in subjects with a Full Mayo score of 6 to 12 at Baseline.
- Achievement of clinical remission per Full Mayo score over time in subjects with a Full Mayo score of 6 to 12 at Baseline (at visits with endoscopy).
- Achievement of SFS = 0, RBS = 0, and ESS = 0 over time (at visits with endoscopy).
- Achievement of SFS = 0, RBS = 0, and ESS \leq 1 over time (at visits with endoscopy).
- Time to clinical response per Partial Adapted Mayo.
- Achievement of SFS \leq 1 over time.
- Achievement of RBS = 0 over time.
- Change from Baseline in RBS over time.
- Change from Baseline in SFS over time
- Achievement of histologic-endoscopic mucosal improvement over time (at visits with endoscopy).
- Achievement of histologic remission over time (at visits with endoscopy).
- Achievement of mucosal healing (endoscopic and histologic remission) over time (at visits with endoscopy).
- Change from Baseline in number of extraintestinal manifestations (EIM) over time (as captured in the EIM electronic case report form [eCRF]).
- Change from Baseline in fecal calprotectin (FCP) over time.
- Achievement of FCP below 150 mg/kg over time.
- Achievement of FCP below 250 mg/kg over time.
- Change from Baseline in high sensitivity C-reactive protein (hs-CRP) over time.
- Achievement of no nocturnal bowel movements at Week 8 as assessed by the UC symptom daily diary.
Achievement of no nocturnal bowel movements at Week 16 as assessed by the UC symptom daily diary.
- Achievement of no tenesmus at Week 8 as assessed by the UC symptom daily diary.
Achievement of no tenesmus at Week 16 as assessed by the UC symptom daily diary.
- Change from Baseline in number of fecal incontinence episodes per week at Week 8 as assessed by the UC symptom daily diary.
Change from Baseline in number of fecal incontinence episodes per week at Week 16 as assessed by the UC symptom daily diary.

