9.0 Efficacy Analyses

9.1 General Considerations

All efficacy analyses will be conducted on the ITT Population.

The Primary Analysis will be performed after all subjects have completed the Week 8 assessment or withdrawn from the study.

The final analysis will be performed after all subjects have either withdrawn from the study or completed the Week 16 assessment, and completed safety follow-up.

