9.5 Additional Efficacy Endpoints and Analyses

Additional efficacy endpoints described in Section 3.3 will be summarized at scheduled timepoints.

For additional binary endpoints, point estimate and 95% CI using normal approximation will be provided for the response rate of the ABBV-668 group. For additional continuous endpoints, the LS-mean and 95% CI will be reported for the ABBV-668 group using MMRM model, which includes visit, Baseline corticosteroid use (yes vs. no), Baseline

Mayo endoscopic sub-score (2 vs 3), TIM (including biologic and non-biologic) failure (Yes vs No) and Baseline measurement, if applicable. For endpoints with a single post-baseline visit, analysis of covariance (ANCOVA) will be used. Same covariates except for visit will be used. Similar analysis using RTB-MI may be performed as sensitivity analysis.

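### SAP 7.1 splits baseline fecal calprotectin at 250 mcg/kg, 1000-fold below the 250 mg/kg endpoint cut-off, so the row cannot show how many subjects started below that cut-off

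*SAP*

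**What the plan says.** SAP 7.1 lists baseline FCP twice. Among the continuous variables it is "Fecal Calprotectin (μ g/g", in micrograms per gram. Among the categorical variables it is "Baseline fecal calprotectin (≥ 250 mcg/kg, < 250 mcg/kg".

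The efficacy cut-offs are in a different unit. SAP 3.3 has "Achievement of FCP below 250 mg/kg over time" and a companion endpoint at 150 mg/kg. Protocol 3.4 has the same pair, for example "Achievement of FCP below 150 mg/kg over time".

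Neither FCP achievement endpoint carries a condition on the Baseline value. SAP 9.1 states: "All efficacy analyses will be conducted on the ITT Population". SAP 4.0 defines that set: "The ITT Population consists of all subjects who received at least 1 dose of study drug". SAP 9.5 gives the analysis: "For additional binary endpoints, point estimate and 95% CI using normal approximation will be provided for the response rate of the ABBV-668 group". The eligibility criteria in Protocol 5.1 require an Adapted Mayo score of 5 to 9 and a centrally confirmed endoscopic subscore of 2 or 3. They set no minimum FCP.

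**The concern.** A baseline split at 250 reads as the row meant to show how many subjects entered above and below the looser endpoint cut-off. In mcg/kg it cannot do that. It also contradicts the unit given for the same variable a few lines earlier.

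The row has some use in this design. The trial is single-arm and open-label, and SAP 9.5 plans only the ABBV-668 rate for additional binary endpoints. The external placebo data in SAP Appendix D Table D-1 cover secondary endpoints, not FCP. To read an FCP achievement rate, one needs to know what share of subjects was already below the cut-off before the first dose. The row as written will not supply it.

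**Working it through.** **1. Units.** 1 mg/kg = 1000 µg / 1000 g = 1 µg/g. 1 mcg/kg = 1 µg / 1000 g = 0.001 µg/g.

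| Place | As written | In µg/g |
|---|---|---|
| SAP 7.1, continuous | µg/g | µg/g |
| SAP 7.1, categorical | 250 mcg/kg | 250 × 0.001 = 0.25 |
| SAP 3.3 and Protocol 3.4, looser cut-off | 250 mg/kg | 250 |
| SAP 3.3 and Protocol 3.4, stricter cut-off | 150 mg/kg | 150 |

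Ratio of the looser cut-off to the categorical split: 250 / 0.25 = 1000. Ratio of the stricter cut-off to the split: 150 / 0.25 = 600.

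**2. What the row would show.** A subject enters the lower class only with a value under 0.25 µg/g, which is 600 times below even the stricter success cut-off. Anyone from 0.25 up to just under 250 µg/g is labelled as at or above the split although already below the looser endpoint cut-off. Essentially all subjects land in one class.

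**3. Where the split is used.** It is a descriptive baseline category. SAP 9.6 names three subgroup factors (corticosteroid use, endoscopic subscore, prior targeted immunomodulator failure), and FCP is not among them. The models in SAP 9.2.2 and 9.5 use those same three factors plus the continuous Baseline measurement. The endpoint cut-offs themselves agree between the protocol and the SAP.

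**4. How the achievement endpoints count.** There is no FCP entry minimum, the set is all dosed subjects, and there is no baseline condition. A subject below a cut-off at Baseline who is still below it at a visit is therefore a responder at that visit. There are two exceptions. A missing value becomes non-response (SAP 9.2.1), and a value on or after ICE2, the start or escalation of UC corticosteroids or start of a targeted immunomodulator, also counts as non-response (SAP 8.0).

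**5. Form of the carry-over (illustration only).** Let b be the share already below the cut-off at Baseline, all assumed to stay below with observed values and no ICE2. Let r be the rate among the rest. Then

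ITT rate = b + (1 − b) × r.

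With the planned 40 subjects, each such subject adds 1/40 = 2.5 percentage points to b. The documents give neither b nor r, so both are assumptions here.

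| b (of 40) | ITT rate if r = 0 | ITT rate if r = 10% |
|---|---|---|
| 5% (2) | 5% | 0.05 + 0.95 × 0.10 = 14.5% |
| 10% (4) | 10% | 0.10 + 0.90 × 0.10 = 19% |
| 20% (8) | 20% | 0.20 + 0.80 × 0.10 = 28% |
| 30% (12) | 30% | 0.30 + 0.70 × 0.10 = 37% |

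The table shows why the Baseline share is worth printing. It does not estimate that share.

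**The case against.** The unit slip is hard to defend, but there is a good case that it matters little. It feeds one table row, no efficacy result is computed from it, and a table with everyone in one class would probably be noticed. That stands as a limit on importance. It is no reason to leave a wrong category in the SAP.

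A reader might infer that the slip conceals the baseline picture altogether. It does not. SAP 7.0 and 7.1 also give the mean, standard deviation, median, minimum and maximum of baseline FCP. The minimum shows whether anyone started below 250 µg/g, and the median shows on which side of it the middle lies. Change from Baseline in FCP is a separate endpoint, to which a subject with no change contributes zero. What is missing is the share below each cut-off.

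A reader might also infer that omitting a baseline condition from the FCP endpoints is itself an error, because the same list has "Achievement of clinical response per Full Mayo score over time in subjects with a Full Mayo score of 6 to 12 at Baseline". The documents do not support this, for two reasons.

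- Endpoints that describe a state, with no baseline condition, are the plan's convention. Stool frequency subscore of 1 or less and rectal bleeding subscore of 0 are listed the same way, and eligible subjects can meet either at entry: 1 + 1 + 3 = 5 has a stool subscore of 1, and 2 + 0 + 3 = 5 has no bleeding.
- The Full Mayo condition does not remove subjects who already meet the endpoint. Entry needs an Adapted Mayo score of at least 5, and Full Mayo adds a physician's global score of 0 to 3, so every eligible subject has at least 5. Remission needs 2 or less, and response needs a fall from Baseline. Nobody eligible meets either at Baseline.

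Nor does a subject who starts low automatically achieve the endpoint at every visit, given the handling of missing values and ICE2. Staying below is also not the same as no change: a fall from 240 to 40 mg/kg would be counted as staying below.

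**Conclusion.** The unit in the categorical row of SAP 7.1 is wrong as written. The factor of 1000 is exact and rests on no assumption. That essentially all subjects would fall in the upper class follows from how far 0.25 µg/g lies below the plan's own success cut-offs.

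The absence of a baseline condition on the two FCP achievement endpoints is not an error. It leaves room for a cheap improvement, because the rate has no comparator and includes subjects who start and stay below the cut-off.

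It would be tempting to attach a number of percentage points to that carry-over. The documents give no baseline FCP distribution and no rate of staying below, so any such number would be only an assumption.

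The reach is one descriptive baseline row and two additional endpoints. No primary or secondary result changes.

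**What to change.** **Correction (SAP 7.1).** Replace mcg/kg with mg/kg in both halves of the categorical FCP row, noting that mg/kg equals µg/g, and add a second split at 150 mg/kg so that both endpoint cut-offs are represented. This costs a wording change and one table row.

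**Improvement (SAP 3.3 and 9.5).** Keep the all-ITT achievement rates. Beside each, show the percentage of subjects below that cut-off at Baseline, and add the rate among subjects at or above it at Baseline: 250 mg/kg for one endpoint, 150 mg/kg for the other. Baseline FCP is already scheduled, so no new data are needed. The subset has a smaller denominator and a wider interval, and it drops subjects with missing Baseline FCP, whose number should be stated.
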